### 8.4.3.3.1 GRAFT-VERSUS-HOST DISEASE

GVHD is an unexpected but potential complication of this therapy. Patients will be monitored for GVHD until donor T-cell chimerism decreases to <5% or 1 year from infusion, whichever comes first.

Acute GvHD shall be graded clinically according to the criteria developed by the consensus conference on acute GvHD (see Appendix D).(96) All suspected cases of acute GvHD must be confirmed histologically by biopsy of an affected organ (skin, liver, or gastrointestinal tract). For purposes of reporting, a pathologist will be ultimately responsible for determining whether a patient does or does not have histologic evidence of GvHD. Diarrhea and/or hyperbilirubinemia in a patient with histologically documented skin GvHD may be assumed to be a manifestation of visceral GvHD and will be graded as such. All patients with histologically documented, clinical grade >2 acute GvHD should receive initial treatment with corticosteroids according to institutional preference. If skin GvHD resolves with treatment but suspected visceral GvHD does not, biopsy of the affected organ (liver or gastrointestinal tract) should be obtained to rule out other causes of hyperbilirubinemia and/or diarrhea. Steroid refractory acute GvHD will be treated according to institutional preferences.

The following information shall be collected on all patients with acute GvHD:

- Date of onset (defined as the date of first biopsy confirming GvHD)
- GvHD evaluation form at the time of onset, weekly until GvHD resolves, and/or day 56
- Initial overall clinical grade
- Maximum overall clinical grade
- Date of onset of grade 3-4 acute GvHD, if any
- The occurrence and severity of acute and chronic GvHD after day 56 will be captured at the patient's sixmonth evaluation.

All instances of grade 2-4 acute GvHD will be captured as serious adverse events.

Chronic GvHD is not an expected complication of the investigational therapy as the DLI should not result in long-term engraftment. Nonetheless, monitoring for chronic GvHD will follow the same procedures as acute GvHD with the following exceptions:

- The severity of GvHD will be determined based on NIH 2014 Consensus Guidelines (see Appendix F).(97)
- Systemic therapy with corticosteroids will be indicated for any patient with moderate or severe chronic GvHD.
- Adjunctive immunosuppressive therapies for severe or steroid refractory chronic GvHD will be determined by the primary provider and institutional preference.

#### 8.4.3.3.2 DONOR LYMPHOCYTE INFUSION-INDUCED APLASIA

DLI-induced aplasia is defined as neutropenia (ANC <500/mL) on day 42 with evidence of donor chimerism (>5%) on the day 42 sample collection. In the case of DLI-induced aplasia diagnosed on day 42, a second chimerism analysis will be sent on day 56 to confirm. All cases of DLI-induced aplasia persisting to day 56 will be reported as serious adverse events.

#### 8.4.3.3.3 CYTOKINE RELEASE SYNDROME

CRS is a recognized complication of the infusion of HLA-mismatched lymphocytes.(51, 98) CRS comprises a constellation of symptoms and signs including fever, hypotension, fluid extravasation leading to edema, ascites and hypoxia, diffuse erythema, diarrhea, and kidney dysfunction. The syndrome is accompanied by elevation in serum markers of inflammation including elevations in acute phase reactants such as interleukin-6, ferritin, and soluble IL-2 receptor. Recent reports demonstrate that CRS can be managed effectively, and symptoms mitigated, by treatment with the anti-IL-6 receptor antibody tocilizumab. (98) Grading of CRS and guidelines for treatment to be used in this study are included in Appendix C.(75) Any instances of CRS grade ≥3 will be reported as serious adverse events.

### 8.4.3.4 RELATIONSHIP TO STUDY INTERVENTION

For all collected AEs, the clinician who examines and evaluates the participant will determine the AE's causality based on temporal relationship and his/her clinical judgment. The degree of certainty about causality will be graded using the categories shown below.

- Definitely Related There is clear evidence to suggest a causal relationship, and other possible
  contributing factors can be ruled out. The clinical event, including an abnormal laboratory test result,
  occurs in a plausible time relationship to drug administration and cannot be explained by concurrent
  disease or other drugs or chemicals. The response to withdrawal of the drug (dechallenge) should be
  clinically plausible. The event must be pharmacologically or phenomenologically definitive, with use of
  a satisfactory rechallenge procedure if necessary.
- Probably Related There is evidence to suggest a causal relationship, and the influence of other
  factors is unlikely. The clinical event, including an abnormal laboratory test result, occurs within a
  reasonable time after administration of the drug, is unlikely to be attributed to concurrent disease or
  other drugs or chemicals, and follows a clinically reasonable response on withdrawal (dechallenge).
  Rechallenge information is not required to fulfill this definition.
- **Possibly Related** There is some evidence to suggest a causal relationship (e.g., the event occurred within a reasonable time after administration of the trial medication). However, other factors may have

contributed to the event (e.g., the participant's clinical condition, other concomitant events). Although an AE may rate only as "possibly related" soon after discovery, it can be flagged as requiring more information and later be upgraded to "probably related" or "definitely related," as appropriate.

- Unlikely to be related A clinical event, including an abnormal laboratory test result, whose temporal
  relationship to drug administration makes a causal relationship improbable (e.g., the event did not
  occur within a reasonable time after administration of the trial medication) and in which other drugs or
  chemicals or underlying disease provides plausible explanations (e.g., the participant's clinical
  condition, other concomitant treatments).
- **Not Related** The AE is completely independent of study drug administration, and/or evidence exists that the event is definitely related to another etiology. There must be an alternative, definitive etiology documented by the clinician.

#### 8.4.3.5 EXPECTEDNESS

The PI will be responsible for determining whether an AE is expected or unexpected. An AE will be considered unexpected if the nature, severity, or frequency of the event is not consistent with the risk information previously described for the study agent.

# 8.4.4 TIME PERIOD AND FREQUENCY FOR EVENT ASSESSMENT AND FOLLOW-UP

The occurrence of an AE or SAE may come to the attention of study personnel during study visits and interviews of a study participant presenting for medical care, or upon review by a study monitor.

AEs can be spontaneously reported or elicited during open-ended questioning, examination, or evaluation of a patient.

Grade 3-5 AEs, including local and systemic reactions not meeting the criteria for SAEs, will be captured on the appropriate CRF. Information to be collected will include event description, time of onset, clinician's assessment of severity, relationship to study product (assessed only by those with the training and authority to make a diagnosis), and time of resolution/stabilization of the event. All AEs occurring while on study must be documented appropriately regardless of relationship. All AEs will be followed to adequate resolution.

Any medical condition that is present at the time that the participant is screened will be considered as baseline and not reported as an AE. However, if the study participant's condition deteriorates at any time during the study, it will be recorded as an AE.

Changes in the severity of an AE will be documented to allow an assessment of the duration of the event at each level of severity to be performed. AEs characterized as intermittent require documentation of onset and duration of each episode.

All events beginning with start of study intervention until the first event of either starting allogeneic transplant conditioning, confirmed disease relapse, death, or 1 year from the of the trial cell infusion will be reported. At each study visit, the investigator will inquire about the occurrence of AE/SAEs since the last visit. Events will be followed for outcome information until resolution or stabilization.

#### 8.4.5 AE REPORTING

The PI and/or the research nurse will monitor each patient closely for the development of adverse events and toxicities and record all such events. AEs will be recorded and reported in our annual report. As some toxicities are expected from the chemotherapy, we will compare incidence of toxicities to historical experience when using chemotherapy without the investigational DLI product. The FDA require the timely reporting of adverse events (including toxic deaths).

Each individual sign or symptom must be documented separately. Grade 3-5 adverse events (both expected and unexpected) will be captured on the appropriate study-specific CRFs.

An investigator must verify the attribution of all adverse events. Evaluation of laboratory toxicities may be documented on CRF provided the investigator signs it. However, if an action was conducted due to this abnormality (e.g., red blood cell transfusion due to low hemoglobin) this would be recorded on the AE form also.

AE reporting will begin at the time of cell infusion and continue through 1 year from day 0 or until loss to followup, death, disease progression, or proceeding to allogeneic BMT, whichever comes first. Subjects who proceed to allogeneic BMT will come off of the trial and will no longer be followed for AEs.

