# 1.3 SCHEDULE OF ACTIVITIES (SOA)

For explanation of procedures, please see Section 8 (Study Assessments and Procedures).

· · · · · · · · · · · · · · · · · · ·	Initial	Allowable time from start of induction	Starting Day 0	Day 28	Day 42	Day 56	6 months +/- 2 weeks	1 yr +/- 2 weeks
History and physical	Х	Within 30 days			Х	Х	X	X
Performance status	Χ	Within 30 days						
Staging Bone Marrow Biopsy and aspirate for research	Х	Within 30 days			X a			
Peripheral blood for research	Х		Daily days 0-7		X a			
CBC & Diff	x	Within 7 days	ANC<50 0- 3x/week ANC≥50 0- weekly to day 56		×	×	×	x
СМР	Х	Within 7 days	Weekly to day 56		Х	Х	Х	Х
CXR or Chest CT	Х	Within 30 days						
Pregnancy test (women, childbearing age)	Х	Within 30 days						
Human Immunodeficiency Virus	Х	Within 30 days						
EKG	Х							
MUGA or ECHO	Х	Within 30 days						
HLA typing	Χ							
Anti-donor HLA antibody testing	Χ				Χ			
Adverse Event Monitoring			Weekly to day 56		х	х	×	X
GvHD evaluation			At onset, weekly until resolves		х	х		
Peripheral blood or bone marrow for donor chimerism					Xa	Xp		
CMV IgG	Х	Within 30 days						
CMV PCR			Weekly through day 56					
C Reactive Protein	Х	Within 7 days	Weekly through day 56		_			
Ferritin	Х	Within 7 days	Weekly through day 56		х	х		

Abbreviations: ANC, absolute neutrophil count; CBC, complete blood count; CMP, comprehensive metabolic panel; CMV, cytomegalovirus; CXR, chest radiograph; CT, computerized tomography scan; diff, differential blood count; ECHO, echocardiogram; EKG, electrocardiogram; GvHD, graftversus-host disease; MUGA, multigated acquisition; PCR., polymerase chain reaction

Tracking of days begins from day of cell transfusion (eg, Day 56 is 56 days after initial cell infusion). Day of cell transfusion is marked as Day 0. Procedures can be performed  $\pm$  3 days from marked date, unless otherwise specified. aSpecified day 42 samples may be performed prior to day 42 if the patient has recovered from aplasia, defined as ANC >500/µl. Otherwise, the specimen collections will be planned for day 42 +/-3 days. b Day 56 chimerism measurement may be omitted if donor T-cell chimerism is < 5% on first measurement or if whole blood/marrow chimerism is < 5% when T-cell chimerism is not measurable. If donor chimerism >5% on day 56, then the investigator will continue performing monthly GVHD evaluations and chimerism until donor T-cell chimerism decreases to <5% or until 1 year, whichever comes first.

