# 4.3 JUSTIFICATION FOR DOSE

For the dose-escalation portion, a minimum of 2 subjects and a maximum of 18 subjects will be enrolled. There will be 3 dose levels in the dose-escalation portion. MTD is defined as the highest dose level with the probability of DLT less than 33% (DLT events are defined in Section 6). The DLT observation window will be within 56 days following NE-DLI. If none of 3 patients experience a DLT, we will escalate to the next dose level. If one of the 3 patients experiences a DLT, we will enroll 3 additional patients and treat at the same dose level. In this case, if none of these additional 3 patients experiences a DLT, we will escalate to the dosage to next level. If 2 or more patients

among 6 enrolled patients experience a DLT, or 2 or more patients in the 3 patient cohort experience DLT, the dosage level exceeds the MTD and the previous dose level will be declared as the MTD. If the first dose level exceeds the MTD, the study will be suspended. If no subjects experience a DLT at any dose level, the MTD will be level 3 ( $5 \times 10^7$  CD4+ T cells/kg).

The RP2D is defined as the dose level selected to be evaluated in the expansion cohort or future phase II studies and will be equivalent to the MTD determined in the phase 1b portion of the study. Once we determine the RP2D level, we will enroll 10 additional eligible patients and treat with the RP2D level. The goal for this expansion cohort is to evaluate the safety and tolerability for patients who will be treated with NE-DLI in the RP2D dose level, and to evaluate the preliminary efficacy estimate for the ORR. Including the dose-escalation portion in which 3 or 6 enrolled patients will have been treated at the RP2D level, a total of at least 13 patients will be treated at the RP2D level. Based on previous data, (18) the complete response rate using microtransplantation was in the range of 36%-52% for MDS or AML from antecedent MDS patients. Hence, for the phase 2 portion, an ORR of 45% is considered clinically meaningful. With a sample size of 13 patients, if our ORR is 45%, the 95% CI (exact binomial) will be (18-74%); if the ORR is 50%, the 95% CI will be (22-78%).

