# 6.1.3.1 DURATION OF FOLLOW-UP

Patients will be followed for a minimum of 56 days after DLI (day 0 is defined as the date of DLI infusion) and then until initiation of conditioning therapy for allogeneic stem cell transplantation, death, disease progression/relapse, or 1 year following the date of infusion, whichever occurs first. Patients removed from study for unacceptable adverse events or who develop treatment-related adverse events will be followed until resolution or stabilization of the adverse event. Patients who proceed to allogeneic stem cell transplantation will be removed from the study.

Post-infusion monitoring: Whole marrow and/or peripheral blood T-cell (CD3) donor cell chimerism will be measured after neutrophil recovery (ANC  $\geq$  500/ $\mu$ l) and no later than the day 42 sample collections to rule out engraftment. If donor chimerism is detected, this test will be repeated on day 56 and then monthly until graft rejection is confirmed. Non-hematologic toxicity will be assessed weekly while subjects are hospitalized, and weekly until day 42.

Disease assessment: Disease restaging requirements are designated in section 1.3.

In addition to disease assessments specified above, results of additional disease assessments performed as standard of care will be collected for study purposes until death or disease progression, whichever occurs first.

Off study criterion is the first event of the following:

- Death
- Disease progression
- One year after infusion (final study visit)

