#### 7.2 PARTICIPANT DISCONTINUATION/WITHDRAWAL FROM THE STUDY

Patients may elect to withdraw from the study at any point without any further justification.

Additionally, patients may be removed from the study at the discretion of their medical providers on the basis of the following criteria:

- Adverse events or any concern that continuing in the study would be harmful
- Need for treatment not allowed in the study, including disease relapse while on study
- Failure by a patient to comply with study protocol
- Onset of pregnancy after enrolling in the study
- Cancellation of the study

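### AE reporting (8.4.5) and the off-study list (6.1.3.1) stop at disease progression with no 56-day floor, in conflict with the protocol's own 56-day minimum follow-up, DLT window and GvHD/chimerism surveillance

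*Combined protocol and SAP*

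**What the plan says.** Four sets of rules bear on how long safety data are collected after the single infusion on day 0.

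- **AE reporting.** Section 8.4.5 starts it at infusion and has it "continue through 1 year from day 0 or until loss to followup, death, disease progression, or proceeding to allogeneic BMT, whichever comes first". Section 8.4.4 runs it "until the first event of either starting allogeneic transplant conditioning, confirmed disease relapse, death, or 1 year".
- **Follow-up and off-study status.** Section 6.1.3.1 begins "Patients will be followed for a minimum of 56 days after DLI", and only then until conditioning, death, progression/relapse or 1 year. The same section closes with a list headed "Off study criterion is the first event of the following": death, disease progression, or one year. Section 7.2 also allows discretionary removal, one ground being "Need for treatment not allowed in the study, including disease relapse while on study".
- **DLT window.** Section 4.3: "The DLT observation window will be within 56 days following NE-DLI". Section 9.4.2 and Appendix F close it earlier if neutrophils have recovered and donor-cell rejection is confirmed. None of the three closes it at progression.
- **GvHD and chimerism.** Section 8.4.3.3.1: "Patients will be monitored for GVHD until donor T-cell chimerism decreases to <5% or 1 year from infusion, whichever comes first". Section 1.3: "If donor chimerism >5% on day 56, then the investigator will continue performing monthly GVHD evaluations and chimerism", to below 5% or 1 year. Progression is not an end point in either.

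**The concern.** NE-DLI is given once, so progression does not end exposure to the donor cells as stopping a repeated drug would. A rule that closes reporting at progression can therefore close it while donor cells are still present. Staff with such a patient cannot obey every section.

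The trial hypothesis is an antitumor effect without GvHD, the primary endpoint is an MTD built on DLT counts, and AEs and GvHD are secondary endpoints. If the shortest rule is followed, part of the DLT window may go unobserved in a patient who is still counted, and later safety data are cut at progression. Progression is also not cleanly separate from toxicity: the criteria in Appendix B include falling granulocytes or platelets and transfusion dependence, so the exit can coincide with the cytopenia in which DLI-induced aplasia has to be excluded. Section 9.3 defines no analysis population, and no rule says whether a patient who progresses inside the DLT window is evaluable or replaced.

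**Working it through.** The plan states no figure on this point, so the check is mainly a comparison of text.

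**1. One patient under each rule.** Take a patient who progresses on day 35 without having been in remission, with neutrophils not recovered and no chimerism result yet.

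| Rule | Status after day 35 |
|---|---|
| 8.4.5 | AE reporting closed |
| 6.1.3.1, off-study list | Off study |
| 6.1.3.1, first sentence | Followed to at least day 56 |
| 8.4.4 | Open on a literal reading: Appendix B defines relapse (after CR or PR) separately from progression |
| 4.3, 9.4.2, Appendix F | DLT window open to day 56 unless rejection is confirmed first (4.3 has no early close) |
| 1.3, 8.4.3.3.1 | GvHD monitoring continues; chimerism is due by day 42 and, unless below 5%, again on day 56 |

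**2. What other rules still secure.**

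- SAEs are reported to 4 weeks after the last dose (8.4.2). With one infusion on day 0, that is about day 28.
- Any death in the first 56 days is an SAE (8.4.3.3).
- Grade 2-4 acute GvHD (8.4.3.3.1) and aplasia persisting to day 56 (8.4.3.3.2) are SAEs.
- Treatment-related events already begun are followed to resolution or stabilization (6.1.3.1).

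**3. What remains.**

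- New non-serious AEs: nothing assures their reporting from progression to day 56.
- New non-fatal SAEs: the 8.4.2 window ends about day 28, leaving days 29 to 56, which is 56 − 28 = 28 days at most. For grade 2-4 GvHD and aplasia in that period, the SAE rules compete with 8.4.5 and the off-study list.
- The delayed-recovery DLT (6.1.4) needs neutrophil data to day 56 plus chimerism. Aplasia is defined on day 42 and confirmed on day 56. Both lie beyond the 4-week SAE window. Section 1.3 also lets study tests be omitted in relapsed patients.
- After day 56: up to 365 − 56 = 309 days of GvHD/chimerism surveillance conflict with the off-study list, but only while donor chimerism is not below 5%.

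**4. Direction of bias in dose finding.** Under the 9.4.2 rule, with q the observed DLT probability,

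P(escalate) = (1−q)³ + 3q(1−q)² × (1−q)³.

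Let p be the true DLT rate and m the share of DLTs missed, so q = p(1−m). The values of p and m are assumptions.

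- p = 0.30, m = 0: 0.343 + 0.441 × 0.343 = 0.494.
- p = 0.30, m = 0.20, so q = 0.24: 0.439 + 0.416 × 0.439 = 0.622.

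| True DLT rate | 0% missed | 10% missed | 20% missed | 30% missed |
|---|---|---|---|---|
| 30% | 49.4% | 55.7% | 62.2% | 68.7% |
| 40% | 30.9% | 37.8% | 45.4% | 53.6% |

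This shows direction and sensitivity only. No document gives m.

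**The case against.** The strongest reply is that the protocol already catches the events that matter most. The SAE rules in step 2 are not cut off at progression, and GvHD of grade 2-4, aplasia persisting to day 56 and CRS of grade 3 or higher are all named SAEs. A patient who recovers early and has rejection confirmed has a closed DLT window under 9.4.2, so later progression loses no DLT data under that version. Section 8.4.4 stops at relapse, so closure at progression is one of several competing statements and not settled protocol. Removal under 7.2 is discretionary, and 6.1.3.1 still follows patients removed for unacceptable AEs to resolution or stabilization.

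Most of this stands, and it narrows the point. It does not close it: the 4-week window ends before day 42, the death rule covers deaths only, follow-up to resolution covers events already begun, and the SAE labels for GvHD and aplasia do not say that observation continues in a patient whom 6.1.3.1 has taken off study.

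Three stronger readings are tempting, and the documents support none of them:

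- *Late toxicity simply goes unrecorded.* The rules in step 2 contradict that.
- *Progression is the commonest way to leave the trial.* No section gives the split between progression, death, transplant and completion. The 80% without remission after HMA failure (2.2.3.1) is not a progression rate.
- *The short survival quoted in 2.2.3.2 measures how many patients miss the six-month GvHD capture.* Patients who have died miss that visit under any reporting rule.

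**Conclusion.** The contradiction is real and should be reconciled. Sections 8.4.5 and 6.1.3.1 (off-study list) end AE reporting and participation at progression with no floor, and 8.4.4 ends reporting at a differently named event. The 56-day minimum in 6.1.3.1, the DLT window and the conditional GvHD/chimerism surveillance all run past progression.

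The exposed data are limited to the items in step 3. Unrecorded DLTs would favour escalation, but how much is lost depends on how many patients progress before day 56 with rejection unconfirmed and on which rule the site follows, and the documents give neither. The conflict beyond day 56 concerns only patients who progress and still have donor chimerism not below 5%.

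**What to change.** This is a change to data collection only. Reconcile 1.3, 6.1.3.1, 7.2, 8.4.2, 8.4.3.3.1, 8.4.4 and 8.4.5 with the 56-day minimum already stated:

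- Before day 56, progression or relapse does not end AE/DLT data collection. Death, withdrawal of consent, loss to follow-up and start of transplant conditioning remain exits, with AE, GvHD and latest chimerism status recorded at exit. Keeping the conditioning exit avoids mixing events from a second donor's graft into the NE-DLI record.
- After day 56, state that progression alone does not end the GvHD/chimerism data collection that 1.3 and 8.4.3.3.1 already require while donor chimerism is not below 5%.
- Use one trigger term, progression or relapse, in 8.4.4 and 8.4.5.
- Record the start date of any new anti-leukaemic therapy, so that later events can be attributed.

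The cost is protocol wording and a few more entries per progressing patient, at one site with at most 28 patients. Chimerism needs a sample and not just a chart entry, and 1.3 allows tests to be omitted in relapsed patients, so a test not done should be recorded as such. Some later events will be confounded by new therapy. The recorded start date helps with that but does not remove it.
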